For event/measurement occurring on or after Day 1, the study day will be calculated as:

$$\text{Study Day} = (\text{Date of event/measurement} - \text{Date of first study drug administration}) + 1.$$

End of treatment (EOT) date: EOT date is the date of the last dose of VIR-2218, VIR-3434 and PEG-IFNa.

EOT assessment: The earliest available assessment on or after EOT date.

EOT + 24 weeks assessment: The earliest available assessment on or after EOT + 161 days.

Treatment Period and Follow-Up Period: Treatment Period and Follow-Up Period are defined in the protocol.

Treatment-emergent (TE) Period: The TE Period is defined as the time period on or from the start of study intervention(s) until the last dose of VIR-2218 + 30 days, or VIR-3434 + 24 weeks, or PEG-IFN α + 30 days, or TDF/TD + 30 days, whichever is later. The TE Period will be used for safety analysis.

Post-TE Period: The Post-TE Period is defined as the time period after the TE Period through the end of Follow-Up Period.

Analysis windows: The analysis window rules for protocol-defined visits are provided in [Appendix 2](#).

Unscheduled visits: Unscheduled visit measurements will be included in the analysis as follows:

1. In planned visit windows as specified, the analysis window rules described in [Appendix 2](#), if applicable.
2. In the derivation of the baseline.
3. In the derivation of maximum and minimum values, or maximum and minimum change from baseline values during the Treatment Period and Follow-Up Period for efficacy analyses, or worst values/grades during the TE Period for safety analyses.
4. In individual participant data listings as appropriate.

Repeated observations: Measurements recorded at different time points are defined as repeated observations. If an assessment has planned repeated measurements, then statistical summaries will present all planned time points, as appropriate.

If there are multiple records at a single assessment date, regardless of whether scheduled or unscheduled visit, the latest record will be used for the analysis.

Missing data handling conventions:

- Missing data can occur due to study withdrawal or participants lost to follow-up before the completion of the study or due to intermittent missing values (i.e., data between two non-missing assessments).
- Missing data in the by-participant data listings will be presented as missing.

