4.3.1. Primary Endpoint

The primary efficacy endpoint is the proportion of participants achieving suppression of HBV DNA (< LLOQ) with HBsAg loss (< 0.05 IU/mL) at EOT. The LLOQ for HBV DNA is 20 IU/mL.

The number and proportion of participants achieving the combined response variable – the suppression of HBV DNA (< LLOQ) with HBsAg loss (< 0.05 IU/mL) – at EOT will be summarized, and the two-sided 95% exact Clopper-Pearson confidence interval (CI) will be calculated for each cohort.

If a participant misses HBV DNA or HBsAg at EOT, then this participant will be considered not meeting the primary endpoint.

HBV DNA and HBsAg values will be provided in a by-participant listing.

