4.4. Secondary Endpoints Analysis

4.4.1. Secondary Efficacy Endpoints

The analysis of the following secondary endpoints will be conducted based on the FAS, unless otherwise specified. The numbering in the table below is consistent with the numbering of the endpoints in [Table 1](#). HBeAg, anti-HBsAg, and anti-HBeAg values will be provided in a by-participant listing.

Secondary Endpoints	Analysis Methods

 2. Proportion of participants with serum HBsAg ≤ 10 IU/mL at the EOT 3. Proportion of participants with serum HBsAg ≤ 10 IU/mL at 24 weeks post-EOT 8. Proportion of participants with HBsAg loss with anti-HBs seroconversion at EOT and at 24 weeks post-EOT 10. Proportion of participants achieving HBsAg loss (< 0.05 IU/mL) 
 a. at EOT b. at 24 weeks post-EOT 	
The number and proportion of participants for each endpoint will be summarized at each visit by cohort, and the two-sided 95% Clopper-Pearson CI will be calculated for each cohort.

 4. Serum HBsAg levels and change from baseline across timepoints in the study 5. Serum HBsAg level at nadir during the study 14. Mean change in serum HBsAg level from baseline across timepoints in the study 	
The observed values and the absolute change from baseline values in both IU/mL and \log_{10} IU/mL of HBsAg
 
at each visit up to end of study (EOS)
 
at nadir during the study
 
will be summarized using descriptive statistics (n, mean, SD, median, Q1, Q3, min, max) by cohort.
 
In addition, the change from baseline in \log_{10} IU/mL at each visit will be plotted for each participant by cohort.
 
Absolute value in \log_{10} IU/mL at each visit will be plotted for each participant by cohort.
 
Mean change from baseline in \log_{10} IU/mL at each visit will be plotted for each cohort.

6. Time to achieve nadir of serum HBsAg during the study
 
7. Time to achieve serum HBsAg loss (< 0.05 IU/mL)
	
Time-to-nadir of serum HBsAg during the study period (up to EOS) will be summarized as a continuous variable by cohort.
 
Time-to-HBsAg loss will be summarized as a continuous variable by cohort.

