
9. Proportion of participants achieving sustained suppression of HBV DNA (< LLOQ) with HBsAg loss (< 0.05 IU/mL) after discontinuation of all treatment:
 
a. at 24 weeks
 
b. at the F48 Follow-Up visit
 
11. Proportion of participants achieving sustained suppression of HBV DNA (< LLOQ) after discontinuation of all treatment:
 
a. at 24 weeks
 
b. at the F48 Follow-Up visit
	
Due to early study termination, modification to timepoints of a. and b. as below:
 
a) at 24 weeks after discontinuation of all treatments (an analysis window of 168 ± 14 days will be applied to capture data around the 24 weeks timepoint, following the rules in Appendix 2 for data selection)
 
b) at the last Follow-Up visit, for participants who have > 24 weeks of discontinuation, after discontinuation of all treatments
 
c) at the last Follow-Up visit after discontinuation of all treatments (all participants will be included in the denominator)
 
Specifically, for a) and b), the denominator used in the percentage calculation will exclude participants with uncertain NRTI discontinuation status due to early study termination (e.g., no Follow-Up 12 visit).
 
The number and percentage of participants achieving
 
 • sustained suppression of HBV DNA (< LLOQ) • sustained suppression of HBV DNA (< LLOQ) with HBsAg loss (< 0.05 IU/mL) 
will be summarized by cohort with the two-sided 95% Clopper-Pearson CI.
 
In addition, the number and percentage of participants achieving
 
 • sustained suppression of HBV DNA (< LLOQ), allowing transient viremia

	
 • sustained suppression of HBV DNA (< LLOQ) with HBsAg loss (< 0.05 IU/mL), allowing transient viremia where transient viremia is defined as HBV DNA \geq LLOQ or HBsAg \geq LLOQ for \leq 35 days, adapted from the 2022 American Association for the Study of Liver Diseases (AASLD) – The European Association for the Study of the Liver (EASL) functional cure definition (AASLD-EASL, 2022), will be analyzed similarly. 
Similarly, the analyses above will be repeated after replacing “HBsAg loss (<0.05 IU/mL) with “HBsAg < 100 IU/mL”. Accordingly, the transient viremia is defined as HBV DNA \geq LLOQ or HBsAg \geq 100 IU/mL for \leq 35 days, adapted from the 2022 AASLD-EASL partial functional cure definition (AASLD-EASL, 2022).

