4.7.1. Extent of Exposure

Exposure summaries will be based on the Safety Analysis Set and presented by study intervention and by cohort and overall. Duration of exposure and the amount of dosage will be summarized.

Duration of exposure (weeks) of study intervention administration will be estimated as: (last dose date – first dose date + DoseFreq days) /7, regardless of dose interruption. DoseFreq will be 28 and 7 when the dosing frequency is every 4 weeks (Q4W) and once weekly (QW), respectively. DoseFreq for Cohort 3a will be either 56 or 84 when the VIR-3434 dosing is administered either every 8 weeks (Q8W) or every 12 weeks (Q12W), respectively. DoseFreq for TDF/TD that is administered daily will be 1 day. For an exposure duration involving more than one treatment, DoseFreq is the longest dosing frequency.

Duration of exposure will be summarized for all study interventions, including VIR-3434, VIR-2218, TDF/TD, and PEG-IFN α . Duration of exposure will be summarized as a continuous variable using descriptive statistics (n, mean, SD, median, Q1, Q3, min, max) by study intervention and cohort. The number and percentage of participants who received the full dose, dose interruption, dose reduction and study intervention discontinuation will be summarized as appropriate by study intervention and cohort.

The amount of dosage will be summarized as a continuous variable using descriptive statistics (n, mean, SD, median, Q1, Q3, min, max) by study intervention and cohort. All data related to exposure of study drug will be provided in a by-participant listing.

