APPENDIX 2. ANALYSIS WINDOWS FOR STUDY ASSESSMENT

Notes:

- The analysis windows will be applied using the following rules for both scheduled and unscheduled visits:
 - a. If no numerical measurement is available within an analysis window, the measurement will be considered missing for the visit.
 - b. If there is more than 1 numerical measurement available within an analysis window, use the following rules:
 - i. The scheduled visit measurement will be used if it is available;
 - ii. The unscheduled visit measurement closest to the target day will be used unless the scheduled visit is available; or
 - iii. If there are multiple unscheduled visit measurements at the same distance from the target day, the latest measurement will be used.
- For the study assessments, e.g., laboratory, ECG, and vital sign measurements, collected on the date of the first dose of study drug, the following rules will be applied if it cannot be determined whether the measurement is before or after the first dose:
 - a. Scheduled measurement will be treated as a pre-dose observation.
 - b. Unscheduled measurement will be treated as a post-dose observation.
- Analysis Visits: The visit name for analysis purpose is used to report data in tables and figures.
- The Analysis Window is continuous, without leaving any date gaps between visits (no gap date). The Analysis Window boundaries are left exclusive, right inclusive, except specified otherwise.

Table 7: Analysis Windows for Safety, Efficacy, and other Assessments: Treatment Period for Cohort 1a/2a

Study Stage	Screening	Treatment Period												
Visit Week		W1	W4	W8	W12	W16	W20	W24	W28	W32	W36	W40	W44/ EOT	
Visit Day ± Visit Window	D -56 to -1	D1	D8±2	D29±2	D57±2	D85±2	D113±2	D141±2	D169±2	D197±2	D225±2	D253±2	D281±2	D309±2
Analysis Visit	Week 1 Day 1 (Baseline)	Week 1 Day 8	Week 4	Week 8	Week 12	Week 16	Week 20	Week 24	Week 28	Week 32	Week 36	Week 40	Week 44 /EOT	
Analysis Window	< D1 dose time	≥D1 dose time, +7	±14	±14	±14	±14	±14	±14	±14	±14	±14	±14	-14, EOT Date	
HBsAg quantitative, HBV DNA quantification, Liver function tests, Serum chemistry, Hematology, Coagulation parameters.														
Analysis Visit	Week 1 Day 1 (Baseline)		Week 4	Week 8	Week 12	Week 16	Week 20	Week 24	Week 28	Week 32	Week 36	Week 40	Week 44 /EOT	
Analysis Window	< D1 dose time		≥D1 dose time, +14	±14	±14	±14	±14	±14	±14	±14	±14	±14	-14, EOT Date	
Anti-HBs quantitative, HBeAg quantitative, HBcrAg, HBV RNA.														

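### SAP Section 4.1 sets no last eligible day for the EOT or the EOT + 24 weeks assessment, and Section 4.3.1 does not say that the 4.1 definition governs the primary endpoint

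*SAP*

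**What the plan says.** SAP Section 4.1 takes the EOT date as the last dose of VIR-2218, VIR-3434 and PEG-IFNα, and then gives two selection rules: "EOT assessment: The earliest available assessment on or after EOT date" and "EOT + 24 weeks assessment: The earliest available assessment on or after EOT + 161 days". Section 4.10.2 lists both as additions in v2.0.

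The same section says "The analysis window rules for protocol-defined visits are provided in" Appendix 2. For HBV DNA and HBsAg, Tables 7, 9 and 10 there contain an analysis visit labelled EOT that opens 14 days before the target day and closes on the EOT date. Tables 11 to 13 assign later samples to FU Week 1 onward. An empty window is handled thus: "If no numerical measurement is available within an analysis window, the measurement will be considered missing for the visit".

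Section 4.3.1 defines the primary endpoint at EOT and adds: "If a participant misses HBV DNA or HBsAg at EOT, then this participant will be considered not meeting the primary endpoint". It cites neither Section 4.1 nor Appendix 2. For secondary endpoints 2, 3, 8 and 10, Section 4.4.1 says "The number and proportion of participants for each endpoint will be summarized at each visit by cohort".

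**The concern.** A forward-looking rule with no end point weakens the failure rule that follows it. If any later sample exists, the participant is not missing at EOT, and a value taken well after the last dose can be reported as the EOT response. The same applies to endpoints 3, 8 and 10b at 24 weeks post-EOT.

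There is also a loose end about which rule applies. Section 4.1 looks forward from the last dose and the Tables 7, 9 and 10 windows look back, so they share only the last-dose date. A programmer who took the Appendix 2 visit labelled EOT would score some participants differently.

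The supplementary analyses in Section 4.3.2 do not settle this. They remove participants who stopped all interventions early, or who missed or discontinued any dose. A fully dosed participant without a last-dose-day result stays in both.

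**Working it through.** **Day count.** I assume that Follow-Up Day 1 is the EOT date, so days after EOT = follow-up day − 1. The SAP's own figure supports this: the F24 visit is D169 ± 7, its lower edge is D162, and 162 − 1 = 161, the number in the 4.1 rule.

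- F1 (D8 ± 2): 7 days, range 5 to 9
- F4 (D29): 28 days
- F24 (D169 ± 7): 168 days, range 161 to 175
- F28 (D197): 196 days
- F36 (D253): 252 days

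**Both rules applied to illustrative patterns** (Cohorts 1a, 2a and 4a, target D309; window open on the left, closed on the right, so it starts after 309 − 14 = D295):

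| Pattern | Section 4.1 selects | Appendix 2 EOT window selects |
|---|---|---|
| Sample on last-dose date D309 | D309 | D309 |
| Week 44 sample D308, last dose D309, F1 D316 | D316 | D308 |
| No usable D309 result, next sample F1 D316 | D316 | none: failure |
| F1 also missed, next sample F4 D337 | D337 | none: failure |
| Only F24 D477 available | D477 | none: failure |
| Last dose at Week 40, D281, sample that day | D281 | none: opens after D295, closes D281 |

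The substitutions differ in weight. F1 lies inside the dosing interval that Section 4.7.1 counts as exposure: "DoseFreq will be 28 and 7 when the dosing frequency is every 4 weeks (Q4W) and once weekly (QW), respectively". F4 falls at the end of that 28-day interval and later visits lie beyond it. (Cohort 3a uses 56 or 84 days.)

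**Cohort 3a.** In Table 8 the Week 36/EOT window is ±14 days and does not close on the EOT date. With last dose on D253 it runs to D267, which is 14 days after EOT and overlaps the FU Week 1 window (D8 + 7 = D15, also 14 days).

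**24 weeks post-EOT.** Table 11 (never stopped NRTI) closes FU Week 24 at D169 + 42 = D211, or 210 days. The next scheduled visit is F36, so a missed F24 gives 252 days under Section 4.1. Tables 12 and 13 (NRTI stopped at F1 or F12) close at D169 + 14 = D183, or 182 days, while Section 4.1 would accept F28 at 196 days. Endpoints 9a and 11a are already bounded: "an analysis window of 168 ± 14 days will be applied to capture data around the 24 weeks timepoint", that is 154 to 182 days, counted from stopping all treatment.

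**Effect of one participant.** Clopper-Pearson 95% limits: lower = Beta(0.025; x, n − x + 1), upper = Beta(0.975; x + 1, n − x).

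- n=15, shift 1/15 = 6.7 points: 2/15 = 13.3% (1.7 to 40.5) becomes 3/15 = 20.0% (4.3 to 48.1)
- n=10, shift 1/10 = 10 points: 1/10 = 10.0% (0.3 to 44.5) becomes 2/10 = 20.0% (2.5 to 55.6)

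These are the initial cohort sizes. Added participants would make each shift smaller.

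**The case against.** The best reply is that the SAP already answers the question of precedence. The two assessments in Section 4.1 are named definitions, written for v2.0, that match the EOT and 24 weeks post-EOT endpoints and have no evident use if Appendix 2 governs those endpoints. Section 4.1 describes Appendix 2 as covering protocol-defined visits. The window for a Week 40 stopper closes before it opens, which shows that it was never meant to derive EOT for early stoppers. The by-visit phrase for endpoints 2, 3, 8 and 10 may mean no more than their two time points. This largely stands, and reduces the rule conflict to a missing cross-reference. A reader might infer that the SAP has two rival primary definitions and an indeterminate primary result; the documents do not support that.

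A second reply is that taking the earliest available result is deterministic, that HBV DNA and HBsAg are scheduled at every treatment visit, and that participant listings would show any substitution. That limits the number affected and makes substitutions traceable. It does not supply a cap, and the SAP saw the need for one in endpoints 9a and 11a.

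A reader might also infer that the rule inflates the response rate. Compared with a capped rule it can only add responders or leave the count unchanged. Compared with the participant's unseen state at EOT, a late sample can err either way, so no direction of bias follows. Nor should weight be put on the lower limits in the examples crossing the 2% reference rate of SAP Section 5, because SAP Section 2 rules out hypothesis testing.

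**Conclusion.** The concern holds in a limited form. The substantive gap is the missing last eligible day in both Section 4.1 rules, which leaves missing-equals-failure with little to act on and lets F4 or later stand for EOT and F36 for 24 weeks post-EOT. The lack of a sentence in Section 4.3.1 naming the governing rule is a smaller gap: it matters for samples not taken on the last-dose date, for early stoppers and for Cohort 3a.

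The documents give no rate of missed last-dose-day samples or early stopping, so the number affected is unknown; it is probably small. The day counts rest on Follow-Up Day 1 being the EOT date, and the visit patterns are illustrations. The protocol supplied is THRIVE's, whereas this SAP is STRIVE's and refers to its own protocol for the Treatment and Follow-Up Periods. Whether that protocol narrows the gap cannot be checked here.

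**What to change.** 1. State in Sections 4.1 and 4.3.1 that the 4.1 assessments govern every EOT and 24 weeks post-EOT endpoint in all cohorts, including Cohort 3a and early stoppers, and that Appendix 2 serves by-visit summaries.
2. Give the EOT assessment one fixed last eligible day, as a number of days after the EOT date chosen by the sponsor and late enough to cover F1 (5 to 9 days). A reference to the end of the FU Week 1 window would not do, because that is 14 days in Tables 11 and 13 but 9 days in Table 12. The existing missing-equals-failure rule then applies after that day.
3. Keep the EOT + 161 days lower bound and add an upper limit, for example EOT + 182 days, counted from the 4.1 EOT date. This covers the whole F24 visit window (161 to 175 days). Only the upper limit should be borrowed from the 168 ± 14 days of Section 4.4.1, since that window has a different anchor and opens at 154 days.

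A footnote counting EOT values not taken on the last-dose date is optional.

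The cost is a few sentences of SAP text and a minor programming change. The downside is that a few participants may become non-responders, including one sampled the day before the last dose who then has no sample by the cap.

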3. ANALYSIS SETS

For the purposes of analysis, the participant analysis sets are defined in **Table 4**.

Table 4: Participant Analysis Set

Participant Analysis Set	Description
All Enrolled Set	The All Enrolled Set includes all participants who signed the informed consent form and were assigned to study intervention. Summaries for disposition, demographics and baseline characteristics will be reported based on the All Enrolled Set.
Full Analysis Set (FAS)	The FAS includes all participants in the All Enrolled Set who received at least one dose of study intervention(s). This set is the primary endpoint analysis set for efficacy and antiviral analyses. Participants will be analyzed according to the study intervention assigned.
Safety Analysis Set	The Safety Analysis Set includes all participants who received any amount of study intervention. All safety analyses will be based on the Safety Analysis Set. Participants will be analyzed according to the study intervention received.
PK Analysis Set	The PK Analysis Set includes all participants in the FAS who had at least one measurable post-dose concentration. The PK Analysis Set will be used for all PK analyses.
Immunogenicity Analysis Set	The Immunogenicity Analysis Set includes all participants in the FAS who had pre-dose and at least one post-dose measurement of immunogenicity, including screening, titers, or neutralizing characterization, as applicable. The Immunogenicity Analysis Set will be used for analyses of the immunogenicity endpoints.

For the efficacy endpoints, no participants in the FAS will be excluded from the efficacy analysis.

Three interim analyses (IAs) will be conducted for each cohort to evaluate the efficacy endpoints at Week 24, EOT, and 24 weeks post-EOT when all participants in the cohort have completed the respective visits. All participants who enrolled or received any amount of study intervention prior to the data cutoff date will be in the scope of the IAs. All data reported on or before the data cutoff date will be included in the IAs. The participant analysis sets for IAs are defined in **Table 5**.

Table 5: Interim Analysis Set

Participant Analysis Set	Description
Interim Full Analysis Set 1 (iFAS1)	The iFAS1 will include participants in the FAS whose scheduled Week 24 Visit is before or on the IA1 data cutoff date.

	This set also includes the FAS participants who prematurely discontinued the study intervention prior to the IA1 data cutoff date.

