- For efficacy response variables, the missing equals failure (MEF) approach will be used for the analysis, except for the sensitivity analysis for the primary endpoint described in [Section Error! Reference source not found.](#). The sensitivity analysis will be conducted to evaluate the impact of missing data, in which missing data will be imputed.
- Missing data will not be imputed, and will be considered as missing data that will not be included in the data summary statistics and analysis. Qualitative data will be imputed as follows:
 1. HBV DNA, for the analysis of the primary endpoint:

- a. If the missing data is reported as “Target Not Detected (TND)”, then the missing data point will be imputed as 0.
- b. If the missing data is reported as “< LLOQ”, then the missing data point will be imputed 1 unit less than the LLOQ value. That’s the LLOQ for HBV DNA is 20 IU/mL, so 19 IU/mL will be imputed.

2. HBs(e)Ag and Anti-HBs(e), for the analyses of primary and secondary efficacy endpoints:
If the missing data is reported as “Not Detected” or “Nonactive”, then the missing data point will be imputed as 0.
3. HBV RNA, for the analysis of an exploratory endpoint:
 - a. If the missing data is reported as “Not Detected”, then the missing data point will be imputed as 0.
 - b. If the missing data is reported as “< LLOQ”, then the missing data point will be imputed 1 unit less than the LLOQ value. That’s the LLOQ for HBV RNA is 0.49 log U/mL, so 0.48 log U/mL will be imputed.
 - c. If the missing data is reported as “> upper limit of quantification (ULOQ)”, then the missing data point will be imputed as 1 unit greater than the value of ULOQ. E.g., The ULOQ for HBV RNA is 6.0 log U/mL, so 6.1 log U/mL will be imputed.
 - d. If the missing data is reported as “Invalid” or “Quantity Not Sufficient (QNS)”, then the missing data will not be imputed and considered as missing data.
4. HBcrAg, for the analysis of an exploratory endpoint:
 - a. If the missing data is reported as “TND”, then the missing data point will be imputed as 0.
 - b. If the missing data is reported as “Target Detected (TD)”, then the missing data point will be imputed as 1 unit less than the LLOQ. That’s the LLOQ is $3.0 \log_{10} \text{U/mL}$, so $2.9 \log_{10} \text{U/mL}$ will be imputed.

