Section 9.4.1: TEAE definition for this sub-protocol: An AE that is reported with an onset date on or after the start of study intervention(s) until end of Follow-Up Period.	TEAE is defined as any AEs reported with an onset date on or after the first dose of study intervention(s) until the end of TE Period. The TE Period is defined as the time period on or from the start of study intervention(s) until the last dose of VIR-2218 + 30 days, or VIR-3434 + 24 weeks, or PEG-IFN α + 30 days, or TDF/TD + 30 days, whichever is later.
Protocol Section 9.5: Three interim analyses will be conducted for each cohort to evaluate the efficacy endpoints at Week 24, EOT, and 24 weeks post-EOT when all participants in the cohort completed the respective visits.	The Sponsor has decided to combine IA1 and IA2. As the study will be terminated earlier, the Sponsor also plans to merge IA3 with the final analysis.

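### STRIVE SAP endpoints 3, 8 and 10b (24 weeks post-EOT) score participants cut off by the sponsor's early termination as failures, which biases the proportion downward if any of them would have responded

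*SAP*

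**What the plan says.** All references are to the STRIVE SAP, v2.0.

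- **Endpoints.** Section 4.4.1 gives endpoint 3 (HBsAg at or below 10 IU/mL), endpoint 8 (HBsAg loss with anti-HBs seroconversion) and endpoint 10b (HBsAg loss) at 24 weeks post-EOT. Each is a proportion with a 95% Clopper-Pearson interval per cohort, on the FAS. Nothing is said about early termination.
- **Missing values.** Section 4.1: "For efficacy response variables, the missing equals failure (MEF) approach will be used for the analysis". The only exception is a sensitivity analysis of the primary endpoint.
- **Denominator.** Section 3: "For the efficacy endpoints, no participants in the FAS will be excluded from the efficacy analysis".
- **Time point.** Section 4.1 defines the 24-week value as "The earliest available assessment on or after EOT + 161 days". It gives no fallback to an earlier visit.
- **Early termination.** Section 4.10.1: "As the study will be terminated earlier, the Sponsor also plans to merge IA3 with the final analysis". In Section 4.4.1, endpoints 9 and 11 receive revised time points and a last-visit version. For their versions a and b, the denominator leaves out "participants with uncertain NRTI discontinuation status due to early study termination (e.g., no Follow-Up 12 visit").
- **Back-up analyses.** Sections 4.4.4 and 4.4.5 plan no sensitivity or supplementary analysis for the secondary endpoints.

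**The concern.** Missing = failure is a reasonable convention when a missing value may reflect how the participant fared, as with withdrawal or loss to follow-up. Those are the causes that Section 4.1 names: "Missing data can occur due to study withdrawal or participants lost to follow-up before the completion of the study". A sponsor's stop date is a different cause. Whether it falls before or after a given participant's 24-week visit depends mainly on when that participant started.

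Under the rule as written, someone with HBsAg below 0.05 IU/mL at EOT and at every later visit up to the stop date is recorded as not having HBsAg loss at 24 weeks post-EOT. In cohorts planned at about 10 or 15, a few such participants move the reported proportion noticeably. No planned sensitivity analysis would show by how much.

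**Working it through.** **1. Can the situation arise under the plan?** In Appendix 2, F12 is Follow-Up day 85 ± 7 and F24 is day 169 ± 7. With EOT as day 1, F24 runs from EOT + 161 to EOT + 175 days (168 − 7 and 168 + 7). Section 4.4.1 gives absence of the F12 visit through termination as its example. Follow-up that stops before F12 cannot supply a value at EOT + 161 days or later. Appendix 2 Tables 11 and 12 open the FU Week 24 window 14 days before day 169, slightly earlier than the Section 4.1 definition, but this does not help a participant who stopped before F12.

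**2. Which rule applies?** Missing = failure, no FAS exclusions, and a time point without fallback together score that participant as a failure on 3, 8 and 10b.

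**3. Planning rates.** SAP Section 5, Table 6 uses HBsAg loss rates of 25% and 40% against a null rate of 2% (exact binomial, one-sided 0.025). Its powers reproduce:

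| n | Responders needed | Actual alpha | Power at 25% | Power at 40% |
|---|---|---|---|---|
| 10 | 2 | 0.0162 | 75.6% | 95.4% |
| 15 | 3 | 0.0030 | 76.4% | 97.3% |

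The two rates are used below only as plausible true values. They describe HBsAg loss, so they fit endpoint 10b best; the relative loss is the same for endpoints 3 and 8.

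**4. Expected reported proportion.** Let p be the true rate, n the cohort size and m the number cut off independently of response. Then

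expected proportion = p × (n − m)/n, and relative loss = m/n.

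m is not in the documents, so a range is shown.

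| n | m | Relative loss | p = 25% | p = 40% |
|---|---|---|---|---|
| 15 | 2 | 13% | 21.7% | 34.7% |
| 15 | 3 | 20% | 20.0% | 32.0% |
| 15 | 5 | 33% | 16.7% | 26.7% |
| 15 | 7 | 47% | 13.3% | 21.3% |
| 10 | 1 | 10% | 22.5% | 36.0% |
| 10 | 3 | 30% | 17.5% | 28.0% |
| 10 | 5 | 50% | 12.5% | 20.0% |

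For example, 25% × 12/15 = 20.0%.

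**5. One possible dataset.** n = 15, 3 cut off, 3 responders among the 12 who could be assessed (95% Clopper-Pearson):

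- missing = failure on the full FAS: 3/15 = 20.0% (4.3 to 48.1)
- cut-off participants excluded: 3/12 = 25.0% (5.5 to 57.2)
- upper bound, if all 3 had responded: 6/15 = 40.0% (16.3 to 67.7)

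**6. Direction.** Counting unknown outcomes as failures can lower the proportion or leave it unchanged. It cannot raise it.

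**The case against.** The strongest case against has five parts.

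- **The harm is conditional.** The documents give no termination date and no count of participants without the visit. If nobody in the FAS was cut off before it, or if none of those cut off would have responded, the bias is zero. This stands, and it limits what can be claimed.
- **The text has a second reading.** Another bullet in Section 4.1 states: "Missing data will not be imputed, and will be considered as missing data that will not be included in the data summary statistics and analysis". Sponsor termination is also not among the named causes of missing data. However, missing = failure is the specific rule for response variables and agrees with Section 3, so the general bullet does not displace it.
- **The third interim analysis had its own set.** iFAS3 starts from participants who completed the 24-week post-EOT visit. But it also admits those who left the study prematurely, and that analysis is now merged with the final one. The visible text does not say that iFAS3 then governs. Parts of Section 4.9 are redacted, so this cannot be settled further.
- **The precedent is narrow.** The exclusion for endpoints 9 and 11 covers uncertain NRTI status only, not everyone cut off, and their version c keeps all participants. This is true. It shows that the sponsor foresaw the problem, not that it adopted a general rule.
- **The data are visible elsewhere.** Section 4.4.1 summarises these endpoints by visit and plots HBsAg per participant, the values are listed, and withdrawal reasons are tabulated. The two intervals in the example also overlap widely. This reduces the harm but does not correct the stated 24-week proportion.

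**Conclusion.** The point holds as a conditional bias in a stated rule. Sponsor cut-off before the 24-week post-EOT visit counts as failure on endpoints 3, 8 and 10b. The proportion is biased downward if any such participant would have responded. If cut-off is unrelated to response, the expected relative loss is the share cut off: 20% with 3 of 15, 30% with 3 of 10. The numbers cut off are assumptions.

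A reader might infer more than the documents support:

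- **That the rates are in fact understated.** This needs at least one cut-off participant who would have responded, and the documents do not show one.
- **That off-treatment response is affected.** EOT is the last dose of VIR-2218, VIR-3434 and PEG-IFNα. Under Section 1.2.4, participants who do not qualify to stop NRTI stay on it, so the accurate term is post-EOT response.
- **That cohorts enrolled later will look worse.** Enrolment order by cohort is not given.
- **That power or a test result suffers.** Section 2 states that no hypothesis testing is done. The harm is to the estimate and its interval, which are what the study reports.

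**What to change.** In Sections 4.4.1 and 4.10.1, for endpoints 3, 8 and 10b:

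1. Report the proportion among FAS participants whose planned 24-week post-EOT visit, including its window to EOT + 175 days, fell on or before the termination date.
2. Calculate that date from the first dose plus the cohort's planned treatment period. From the Appendix 2 visit days this is first dose + 483 days for Cohorts 1a, 2a and 4a (308 + 175), + 511 for 5a (336 + 175), and + 427 or + 455 for 3a (252 or 280, + 175). The exclusion then depends on calendar time only. Using the actual EOT date would keep early treatment discontinuers while removing completers who started on the same day.
3. Keep missing = failure for all other missing values.
4. Show the full-FAS missing = failure result alongside, with the number excluded per cohort.
5. Amend the sentence in Section 3 that rules out any FAS exclusion so that it allows this one.

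The cost is some SAP wording and one flag from dates already collected. The denominator is smaller and the interval wider in affected cohorts. A few early discontinuers with an observed 24-week value would count only in the full-FAS line.
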